12.3. Safety Analyses

All patients who receive a dose of neratinib will be analyzed for safety. The incidence of TEAEs and SAEs for Cycle 1 through 28 days of neratinib monotherapy following the second study colonoscopy procedure in patients with stage 1 to 3c breast cancer treated in the extended adjuvant setting, and following the completion of Cycle 2 in patients with mBC will be summarized after all biopsies have been completed. Following 28 days of neratinib monotherapy after the completion of the second study colonoscopy procedure in patients with stage 1 to 3c breast cancer treated in the extended adjuvant setting, and Cycle 2 in patients with mBC through 28 calendar days after the last administration of neratinib, only SAE data will be collected and summarized.

AEs will be coded using the Medical Dictionary for Regulatory Activities MedDRA coding system and all AEs will be graded by the Investigator according to the NCI-CTCAE version 4.0.

Incidence of AEs will be summarized by system organ class (SOC) and preferred term (PT), and will be summarized by grade. A patient who experiences the same AE more than once within a SOC or preferred term category will be counted only once, using the worst toxicity grade for that event. SAEs will be summarized.

Serious AE and deaths will be provided in a listing. All AEs resulting in discontinuation of neratinib in Cycle 1 through 28 days of neratinib monotherapy following the second study colonoscopy procedure in patients with stage 1 to 3c breast cancer treated in the extended adjuvant setting, and following the completion of Cycle 2 in patients with mBC, dose modification, dosing interruption, and/or treatment delay of investigational product will also be listed and tabulated by PT.

Laboratory test results will be collected at screening and on Day 1/Cycle 1 and Cycle 2. On-study laboratory test abnormalities reported during screening, Cycle 1 and Cycle 2 will be summarized. In subsequent visits only liver function tests will be collected.

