Abbreviations: β-hCG=beta-human chorionic gonadotropin; ALP=alkaline phosphatase; ALT=alanine aminotransferase; AST=aspartate aminotransferase; BUN=blood urea nitrogen; C=cycle; CBC=complete blood count; CRP = C-reactive protein; D=day; ECG= electrocardiogram; ECHO=echocardiogram; ECOG=Eastern Collaborative Oncology Group; eCRF=electronic case report form; EOT = end of treatment; ESR = erythrocyte sedimentation rate; FISH= fluorescence in situ hybridization; Hb=hemoglobin; Hct=hematocrit; IHC=immunohistochemistry; INR = International Normalized Ratio; LFT=liver function test; LDH=lactate dehydrogenase; MUGA=multiple-gated acquisition scan; NP=nurse practitioner; PA=physician's assistant; RBC=red blood cell; SAE=serious adverse event; TEAE=treatment-emergent adverse event; WBC=white blood cell.

^a Cycle 1, neratinib monotherapy, is defined as 28 days. Cycle 2 and all subsequent cycles are defined as 21 days. Cycle 2 will begin after the completion of the second study colonoscopy procedure. The Treatment Discontinuation Visit will be performed as soon as possible, but no later than 3 business days after the last dose and before start of new anticancer regimen. All visit dates are calculated from the date of first dose of neratinib. If a visit occurs before or after a scheduled visit date, the next visit is still expected to occur on the date initially calculated for this visit, and is not shifted due to an earlier or later prior visit.

^b Screening procedures and enrollment may occur on one day, however, enrollment must not be done before all screening procedures have been completed and results confirming eligibility have been reviewed.

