Patients with baseline neutrophil counts of $<1.5 \times 10^9/L$ and/or thrombocyte counts of $<100 \times 10^9/L$ should not be treated with **capecitabine**. If unscheduled laboratory assessments

during a treatment cycle show Grade 3 or 4 hematologic toxicity, treatment with **capecitabine** should be held.

Guidelines for dose adjustments of capecitabine for hematologic toxicity due to combination of neratinib plus capecitabine are shown in **Table A2.6**.

Table A2.6: Hematologic Abnormalities Requiring Dose Adjustment of Capecitabine (When Administered in Combination with Neratinib)

NCI CTCAE v 4.0	Action
Grade 3 Neutrophil: <1000-500/mm ³ ; <1-0.5 x 10 ⁹ /L Platelet: <50,000-25,000/mm ³ ; <50-25 x 10 ⁹ /L Hemoglobin decreased: <8 g/dL; <4.9 mmol/L; <80 g/L; transfusion indicated	
 • Neratinib should be continued at the same dose • Hold capecitabine until event resolves or decreases to Grade 1 or Grade 2 • Reduce next capecitabine dose to 1100 mg/m² (550 mg/m² BID) • If the event recurs a 2nd time, hold capecitabine until event resolves or decreases to Grade 1 or Grade 2 • Reduce next capecitabine dose of 750 mg/m² (375 mg/m² BID) • If the event recurs/persists, discontinue capecitabine permanently.
Grade 4 Neutrophil: <500/mm ³ ; <0.5 x 10 ⁹ /L Platelet: <25,000/mm ³ ; <25 x 10 ⁹ /L Hemoglobin decreased: life-threatening consequences; urgent intervention indicated	
 • Neratinib should be continued at the same dose. • Capecitabine should be discontinued permanently OR if the Investigator deems it to be in the patient's best interest to continue, hold capecitabine until resolved to Grade ≤ 1 • If the Investigator decides to resume capecitabine, reduce the dose to 750 mg/m² (375 mg/m² BID) • If the event recurs/persists, discontinue capecitabine permanently

Abbreviations: BID: twice daily; L=liter; NCI CTCAE v 4.0: National Cancer Institute Common Terminology Criteria for Adverse Events Version 4.0.

Hand and Foot Syndrome

Guidelines for dose adjustments of neratinib and capecitabine for toxicity of Hand and Foot Syndrome (Palmar-Plantar Erythrodysesthesia syndrome) due to combination of neratinib plus capecitabine are show in **Table A2.7**.

Table A2.7: Hand and Foot Syndrome (Palmar-Plantar Erythrodysesthesia Syndrome) Requiring Dose Adjustment of Neratinib and Capecitabine

NCI CTCAE v4.0	Action

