3. DEFINITIONS

Baseline

The baseline value for a parameter of interest is the last measurement obtained prior to or on the date of the first dose of neratinib.

Cycle

The first cycle is 28 days for all subjects, all of whom receive neratinib and loperamide prophylaxis. After the first 28-day cycle, stage 1 to 3c breast cancer patients receiving extended adjuvant treatment return to clinic every 3 months. Metastatic breast cancer patients return to clinic at scheduled 21-day cycles, during with time they receive both neratinib and capecitabine.

Study Day 1

Study Day 1 is the date the first dose of neratinib is taken.

Treatment duration

Treatment duration in days = last dose date - first dose date + 1

Actual Dose Intensity

The actual dose intensity is defined as the cumulative actual dose divided by treatment duration.

Relative Actual Dose Intensity

The relative actual dose intensity is defined as the actual dose intensity divided by the planned dose intensity.

Prescribed Dose Intensity

The prescribed dose intensity is defined as the cumulative prescribed dose divided by treatment duration.

Treatment-Emergent Adverse Event (TEAE)

A TEAE is defined as an AE that occurs or worsens on or after the first administration of neratinib and up to 28 days after the second colonoscopy in patients with stage 1 to 3c breast cancer, and following completion of Cycle 2 in mBC patients.

Investigational Product (IP)

Investigational product (IP) is used to reference neratinib and capecitabine.

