6.9.2 Treatment-Emergent Adverse Events (TEAEs)

A high-level summary of TEAE will be provided and select summaries of TEAE subgroups (indicated in parentheses).

TEAEs will also be presented in incidence tables by system organ class (SOC), preferred term (PT), and grade for the following:

- Any TEAE (summary)
- Treatment-related TEAE
- Serious TEAE
- Serious treatment-related TEAE
- Grade 3 or 4 TEAE (summary)
- Fatal TEAE (summary)
- TEAE leading to dose reduction
- TEAE leading to dose interruption
- TEAE leading to treatment discontinuation

Incidence tables of TEAEs in descending order of frequency by PT will be presented for any TEAE, Grade 3 or 4 TEAE, and fatal TEAE.

Listings will be provided for SAEs, TEAEs, and TEAEs leading to study drug discontinuation.

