9.2 LISTINGS

Listings
Listing of disposition
Listing of deviations

Listing of demographics
Listing of cancer history
Listing of prior anti-cancer medications
Listing of serological parameters
Listing of stool parameters
Listing of neratinib exposure
Listing of capecitabine exposure
Listing of loperamide exposure
Listing of concomitant therapy
Listing of SAEs
Listing of TEAEs
Listing of TEAEs leading to IP discontinuation
Listing of deaths
Listing of laboratory values, blood chemistry
Listing of laboratory values, hematology
Listing of liver function test values
Listing of ECGs
Listing of Vital Signs
Listing of LVEF
Listing of disease recurrence

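### The SAP's adverse-event tables do not separate neratinib alone from neratinib plus capecitabine in metastatic patients, and its IP-discontinuation listing does not name the drug stopped

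*SAP*

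**What the plan says.** **Window.** SAP section 3 starts the TEAE window at the first neratinib dose. It ends 28 days past the second colonoscopy for stage 1 to 3c patients, "and following completion of Cycle 2 in mBC patients". The same section says of the 21-day mBC cycles that "they receive both neratinib and capecitabine". Protocol 12.3 sets the same Cycle 2 limit, so the window is not the SAP's invention.

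**Tables.** SAP 6.9.2 states: "TEAEs will also be presented in incidence tables by system organ class (SOC), preferred term (PT), and grade for the following". SAP 6.9.3 plans an AESI table by preferred term and grade, with the AESIs described as those for neratinib. SAP 6.9.1 summarises treatment-emergent diarrhea by worst grade. Neither these sections nor the table list in 9.1 gives a split by period, regimen or disease setting. Nor is there a Cycle 1 limit on the diarrhea table, although SAP 2.2.2 defines the secondary endpoint on the first 28 days of monotherapy.

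**Discontinuation.** SAP section 3 says "Investigational product (IP) is used to reference neratinib and capecitabine", and SAP 9.2 plans a "Listing of TEAEs leading to IP discontinuation". SAP 6.9.2 calls the same output study drug discontinuation. Protocol 12.3 refers to "All AEs resulting in discontinuation of neratinib in Cycle 1" and the period that follows. SAP section 8 declares no changes from the protocol.

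**The concern.** The trial's endpoints concern neratinib monotherapy. In an mBC patient, a table entry could have arisen under either regimen, and the table will not say which.

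The diarrhea table matters most. SAP 6.9.1 reports the worst grade, and protocol 12.3 counts a patient once at the worst grade. If an mBC patient had mild diarrhea in Cycle 1 and worse diarrhea in Cycle 2, only the Cycle 2 grade would appear. The grade that the secondary endpoint asks for would be lost from the table.

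The discontinuation listing has a separate problem. The protocol's actions can differ by drug. In Appendix 2, Table A2.6 (hematologic toxicity), capecitabine may be stopped permanently while "Neratinib should be continued at the same dose". Under the SAP's definition that event qualifies as an IP discontinuation, although neratinib was not stopped. Protocol 13.1.7 likewise asks for one causality judgement about investigational product, with no drug named.

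**Working it through.** The documents give no figure on this point to reproduce, and the sample size of 3-5 rests on feasibility (protocol 12.5). The check is a count of days.

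**Inputs**
- Cycle 1 is 28 days. For mBC, "Cycle 2 and all subsequent cycles are defined as 21 days" (protocol Appendix 1, Table A1.2 footnotes).
- Second colonoscopy: Day 30 ± 3 (protocol 4.1).
- Capecitabine: Days 1-14 of each 21-day cycle, only after the second colonoscopy (protocol 6.3).
- Assumption: Cycle 2 Day 1 is the later of Day 29 and the day after the colonoscopy.

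**One mBC patient.** Window = (Cycle 2 Day 1 − 1) + 21. Combination share = 21 / window. Capecitabine dosing share = 14 / window.

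| Colonoscopy | Monotherapy days | Window | Combination cycle | Capecitabine dosing days |
|---|---|---|---|---|
| Day 27 | 28 | 49 | 21/49 = 42.9% | 14/49 = 28.6% |
| Day 30 | 30 | 51 | 21/51 = 41.2% | 14/51 = 27.5% |
| Day 33 | 33 | 54 | 21/54 = 38.9% | 14/54 = 25.9% |

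A footnote to Table A1.2 instead places the colonoscopy on Cycle 2 Day 1 (+5 days), so as late as Day 34. That gives 34 + 21 = 55 days and 21/55 = 38.2%, which changes little.

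**Whole trial.** A stage 1 to 3c patient's window is colonoscopy day + 28, or 55-61 days, all on neratinib alone. With the colonoscopy on Day 30 and m mBC patients out of N, the combination share of person-time is 21m / (51m + 58(N − m)).
- N = 3, m = 0 to 3: 0%, 13%, 26%, 41%.
- N = 5, m = 0 to 5: 0%, 7%, 15%, 23%, 32%, 41%.

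For example, with N = 3 and m = 1, 21 / (51 + 116) = 21/167 = 12.6%.

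**Diarrhea window.** The endpoint covers 28 days. The table covers 49-54 days in mBC and 55-61 days in adjuvant patients. It is therefore wider than the endpoint in both groups, but only in mBC does the extra time include capecitabine.

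**Chance that a capecitabine-type event enters the tables.** Protocol 2.3.1.1 reports hand-foot syndrome in 47% of patients on the combination, over whole treatment. Used as an upper bound for one cycle, the chance of at least one event is 1 − 0.53 = 47% with one mBC patient and 1 − 0.53³ = 85% with three. If a quarter of that rate (0.1175) applied in one cycle, which is an assumption, the chances are 12% and 31%.

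**Use of the term investigational product.** Protocol 6.5 names capecitabine beside investigational product. Protocol 6.3.1, on capecitabine dose adjustment, applies the term to capecitabine, and the title of Appendix 2 uses it for tables covering both drugs. The SAP's definition matches one of these usages and not the other.

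**The case against.** A reader might infer that capecitabine toxicity will be reported as neratinib's. The documents do not support that. No text attributes combination-period events to neratinib; the events are simply called treatment-emergent. A reader might also blame the pooling on the IP definition. It comes instead from the TEAE window and the unsplit tables. IP appears in only one planned output title, and its effect is confined to that listing.

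The prior-study rates do not show that capecitabine would inflate the diarrhea figures. Protocol 2.3 gives any-grade diarrhea of 88% on the combination, against 95.4% on neratinib without prophylaxis and 79.6% with loperamide. Hand-foot syndrome has its own preferred-term row and would not distort other rows. One event does move an incidence by 20-33 points at this size (1/5 to 1/3), but that is true of any event.

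The best defence is that the data are mainly to be read from listings (protocol synopsis; SAP section 6). The SAP lists disease setting (6.5.1). It also lists exposure to each drug separately, with indicators for reduction due to AE and dose withheld due to AE (6.7.1, 6.7.2). With 3-5 patients, a reader could probably separate the regimens by hand.

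Much of that stands, and it limits the harm. It does not remove it. The SAP does not give the columns of the TEAE listings, so onset relative to first capecitabine is not assured. The exposure listings carry no indicator for discontinuation due to AE. No listing can recover relatedness by drug unless it was collected that way, and the documents do not show whether the eCRF does so.

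**Conclusion.** The point holds as a gap in the outputs. For mBC patients, the planned TEAE, AESI and diarrhea tables cannot distinguish the two regimens. The diarrhea table does not match the secondary endpoint's window. The IP-discontinuation listing as titled does not answer the question about neratinib in protocol 12.3, and SAP section 8 does not acknowledge the difference.

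Per mBC patient, 39-43% of the TEAE window falls in the combination cycle and 26-29% on capecitabine dosing days. This assumes that Cycle 2 starts as set out above and that the patient completes it. Across the trial the share runs from zero to 41%; no mBC quota is set, so it cannot be narrowed. If no mBC patient enrols, the mixing of regimens disappears and only the over-wide diarrhea window remains. The definitions of both endpoints are unaffected, because capecitabine cannot start before the second colonoscopy.

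**What to change.** In SAP 6.9 and 9:

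1. Present TEAEs, AESIs and diarrhea by onset before versus on or after the first capecitabine dose. At the least, flag the regimen at onset in the TEAE listing.
2. Limit the secondary-endpoint diarrhea summary to Cycle 1. This is a separate cut from item 1, since the pre-capecitabine period can run to Day 33. Label any longer summary as supplementary.
3. Keep every discontinuation, reduction and interruption in the outputs and identify the drug concerned. Restricting the listing to neratinib would match the protocol's sentence but drop the capecitabine-only stops.
4. Report relatedness per drug where it is collected that way.
5. Reconcile the meaning of investigational product between SAP section 3 and protocol 6.5, 6.3.1 and 12.3, and record any remaining difference in SAP section 8.

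The cost is SAP wording and a few columns. If the eCRF does not already record causality and action taken by drug, it would need one field of each per drug. The downside is small cells at N = 3-5 and monotherapy periods of unequal length: about 28-33 days in mBC against 55-61 in adjuvant patients. The tables should therefore show the days at risk in each period.

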4. DATA SCREENING, ACCEPTANCE AND PROGRAMMING

4.1 General Principles

Clinical data are entered into the Medrio database. Data cleaning and query resolution are performed according to the study specific data management plan. Prior to any formal analysis, a data cut-off date will be established by the clinical study team to ensure appropriate cleaning and query resolution of data up to the data cut-off date. Data extracts in SAS formats will be taken from a snapshot of the live database or a locked database will be used for the analyses.

The clinical study team will identify the criteria for important protocol deviations. Important protocol deviations will be summarized and listed in the clinical study report.

4.2 Handling of Missing and Incomplete Data

Missing and incomplete data will be identified for investigation, and possible resolution, as part of the data cleaning. At the analysis time, missing data will be treated as missing, unless otherwise specified. Missing and incomplete dates for adverse events, concomitant medications, and historical data may be imputed for certain analyses.

Partial dates will be defined as dates that are missing certain elements of the date field. This may include missing information for the month, day or year, or two of these elements, but not all three. If either month or year is missing or the date is completely missing then no data imputation will be implemented.

AEs with completely missing start dates will be considered as treatment-emergent adverse events unless there is clear evidence that the AEs start prior to the first dose.

4.3 Testing/Validation Plan

Statistical programming will be performed using SAS software, version 9.4 or higher, on a Windows Server OS. All SAS programs will be documented, QC'ed, written in accordance with department SOPs.

Analyses performed by statistical software other than SAS are permitted if the analyses cannot be readily performed in SAS. All statistical programming must follow commonly accepted practice including adequate comments within the program, code review, logic review, and check of program log. Key analysis results may require additional validation including but not limited to independent programming.

5. ANALYSIS POPULATIONS

5.1 Safety Population

The safety population is defined as all enrolled patients who have received at least one dose of neratinib.

6. ANALYSIS METHODS

A minimum of 2 analyses will be conducted: primary and final. The primary analysis will occur after all patients have completed the second study colonoscopy. The final analysis will occur after all patients have either discontinued or completed study treatment. Unless otherwise indicated, all data will be presented at both analyses and only in the form of listings.

In the case of data summaries, for continuous endpoints, the sample size (n), mean, standard deviation, median, 25th percentile (Q1), 75th percentile (Q3), minimum, and maximum will be provided. For discrete data, the frequency and percent distributions will be provided.

6.1 Disposition of Patients

Reasons for treatment discontinuation and study discontinuation will be listed.

6.2 Deviations

A listing will be provided for protocol deviations.

6.3 Demographic and Baseline Characteristics

A listing will be provided for demographics, which will include age at study enrollment, sex, ethnicity, race, menopausal status, height (cm), weight (kg), and BMI (kg/m²).

6.4 Medical History

Medical history will be listed by system organ class and preferred terms.

6.5 Cancer History

6.5.1 Summary of Cancer History

A listing will be provided. The listing will include ECOG performance status and disease setting.

6.5.2 Prior Anti-cancer Medications

A listing will be provided for prior anti-cancer medications. The listing will include status (yes/no) of prior anti-cancer medication, indication (neoadjuvant, adjuvant, metastatic/locally advanced).

6.6 Serological and Stool Parameters

Listings will be provided for the following parameters: serological inflammatory markers and stool inflammatory markers, along with applicable data elements from each form.

6.7 Study Medications

6.7.1 Study Medication (Neratinib)

Exposure to neratinib during the study will be listed. Variables will include treatment duration in months, cumulative actual dose (mg), actual dose intensity (mg/day), relative actual dose intensity, cumulative prescribed dose, prescribed dose intensity, and compliance. The compliance for neratinib is calculated by using actual dose intensity divided by the prescribed dose intensity.

Indicator for dose reduction (yes/no), dose reduction due to AE (yes/no), and the lowest dose reduction level, will be included in the listing. In addition, indicator for the dose withheld due to AE (yes/no) will be included.

6.7.2 Study Medication (Capecitabine)

A listing will be provided for capecitabine exposure, which will include treatment duration (months), cumulative actual dose (mg/m²), actual dose intensity (mg/m²/day), relative actual dose intensity (%).

Indicator for dose reduction (yes/no) and dose reduction due to AE (yes/no) and the lowest dose reduction level will be included in the listing. In addition, indicator for dose withheld due to AE (yes/no) will be included.

6.8 Concomitant Medications and Therapy

Concomitant medications will be listed by Anatomical Therapeutic Chemical (ATC) category and preferred term.

6.8.1 Loperamide During the First Cycle

Exposure to loperamide during the first cycle (28 days) will be listed by treatment duration (days), cumulative actual dose (mg), actual dose intensity (mg/day) and relative actual dose intensity. In addition, the initial loading dose will also be provided.

The highest daily dose, lowest daily dose, dose reduction due to AE (yes/no), dose increase due to AE (yes/no), and dose hold due to AE (yes/no).

For loperamide, for the first 14 days, the planned dose intensity is 12mg/day; for days 15 through 28, the planned dose intensity is 8 mg/day. The planned dose intensity for loperamide for the first cycle is $(12\text{mg} \times 14\text{days} + 8\text{mg} \times 14\text{days})/28 = 10\text{mg/day}$.

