2.3.3 Loperamide

- The initial dose of loperamide 4 mg will be self-administered orally with the first dose of neratinib.
- During weeks 1-2 (day 1 – 14) of Cycle 1 loperamide 4 mg will be self-administered three time daily.
- During weeks 3-4 (days 15 – 28) of Cycle 1 loperamide 4 mg will be self-administered twice daily
- After the first 28 days, loperamide will be self-administered as needed (PRN) (not to exceed 16 mg per day).

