2.3.4 Loperamide Dose Adjustments

Patients are expected to take loperamide prophylaxis as directed. However, patients may require individualization of loperamide prophylaxis dose (up to a maximum dose of 16 mg per day).

- For patients who develop diarrhea during Cycles 1, loperamide should be increased up to a maximum of 16 mg a day.
- If a patient is unable to tolerate loperamide due to symptomatic constipation, loperamide should be held until after the first bowel movement and then resumed at a dose reduced by one level.
- For recurrent symptomatic constipation events, hold loperamide until after the first bowel movement and then resume at a dose reduced to the next lower dose level.
- If a patient is unable to tolerate once-daily loperamide due to constipation, hold loperamide and discuss subsequent loperamide dosing with the Medical Monitor.
- Neratinib dosing should continue if loperamide is held.

Loperamide dose reduction levels for constipation are:

- Dose Level 0 (4mg TID or 6 tablets/capsules a day)
- Dose Level -1 (4 mg BID or 4 tablets/capsules a day)
- Dose Level -2 (2mg TID or 3 tablets/capsules a day)
- Dose Level -3 (2 mg BID or 2 tablets/capsules a day)
- Dose Level -4 (2 mg once a day or 1 tablet/capsule a day)

If a patient experiences an AE leading to dose interruption of neratinib for reasons other than diarrhea, consider holding loperamide until neratinib treatment is resumed.

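### SAP 6.8.1 compares loperamide intensity over a patient's own days with a fixed 28-day average of 10 mg/day, so full dosing that ends before Day 28 reads above 100% of plan

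*SAP*

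**What the plan says.** SAP 3 builds the measure in three steps:

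- Duration: "Treatment duration in days = last dose date - first dose date + 1".
- Actual intensity: "The actual dose intensity is defined as the cumulative actual dose divided by treatment duration".
- Relative intensity: "The relative actual dose intensity is defined as the actual dose intensity divided by the planned dose intensity".

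SAP 6.8.1 lists these quantities for loperamide over the 28-day first cycle. It gives the schedule in two phases: "for the first 14 days, the planned dose intensity is 12mg/day; for days 15 through 28, the planned dose intensity is 8 mg/day". It then reduces them to one value: "The planned dose intensity for loperamide for the first cycle is" (12 × 14 + 8 × 14)/28 = 10 mg/day. Table 4 in Protocol 6.2 shows the same schedule.

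Nothing in SAP 3 or 6.8.1 gives a different planned value for a patient whose loperamide ends before Day 28.

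The planned start is Day 1. SAP 2.3.3 says "The initial dose of loperamide 4 mg will be self-administered orally with the first dose of neratinib", and SAP 3 says "Study Day 1 is the date the first dose of neratinib is taken".

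**The concern.** The numerator of the ratio covers the days the patient was actually dosed, while the denominator always covers 28 days. That would do no harm if the planned dose were constant. Here it falls by a third after Day 14, so the early days carry a higher plan than the cycle average. Anyone observed only over the early days is compared with too low a target.

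Two things follow for the reader of the listing. A patient who followed the plan exactly and stopped can appear to have exceeded it, and a patient who under-dosed and stopped can appear to have met it. Values above 100% also have a genuine meaning in this trial, because SAP 2.3.4 allows loperamide to be increased up to 16 mg/day. The column cannot tell the two apart.

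For neratinib, SAP 6.7.1 also lists prescribed intensity and a compliance ratio. For loperamide there is neither, so this is the only listed comparison with plan for a mandatory prophylaxis given over the window of the secondary diarrhea endpoint.

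**Working it through.** **Inputs.** Planned dose is 12 mg/day on Days 1-14 and 8 mg/day on Days 15-28 (SAP 6.8.1; Protocol Table 4). The denominator is 10 mg/day (SAP 6.8.1). Duration and intensity are as defined in SAP 3. The initial 4 mg is taken as part of the first day's 12 mg.

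**The plan's own figure.** 12 × 14 + 8 × 14 = 168 + 112 = 280 mg, and 280/28 = 10 mg/day. It reproduces.

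**Full dosing from Day 1, last dose on Day d.** The planned dose to Day d is P(d) = 12 × min(d, 14) + 8 × max(d − 14, 0). The listed ratio is P(d)/d/10.

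| Last dosing day | Planned dose, mg | Calculation | Listed ratio |
|---|---|---|---|
| 3 | 36 | 36/3/10 | 120% |
| 14 | 168 | 168/14/10 | 120% |
| 18 | 200 | 200/18/10 | 111.1% |
| 21 | 224 | 224/21/10 | 106.7% |
| 24 | 248 | 248/24/10 | 103.3% |
| 27 | 272 | 272/27/10 | 100.7% |
| 28 | 280 | 280/28/10 | 100% |

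Every stop day from 1 to 27 gives more than 100%.

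**Any level of dosing.** For cumulative dose C with a Day 1 start, the listed ratio is C/(10d) and the ratio to the dose planned for the same days is C/P(d). Their quotient is P(d)/(10d), so C cancels and the inflation depends only on the last dosing day: 1.20 up to Day 14, 1.067 at Day 21, 1.007 at Day 27, and 1 at Day 28. For example, 140 mg over Days 1-14 is listed as 140/14/10 = 100%, against 140/168 = 83.3%.

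**Two different patients, one value.** A patient who takes 12 mg/day for all 28 days reads 336/28/10 = 120%, the same as a patient who followed the plan and stopped on Day 14. Only the first exceeded plan.

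**Where the rule is not too high.**

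- Hold on Days 8-14, then planned dosing to Day 28: (7 × 12 + 14 × 8)/28/10 = 196/280 = 70%, which is correct.
- Full dosing on Days 2-27: 260/26/10 = 100.0%.
- Full dosing on Days 5-27: 224/23/10 = 97.4%.
- Full dosing on Days 5-28: 232/24/10 = 96.7%.

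A late start therefore offsets the excess or reverses it.

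**Sensitivity to the initial dose.** SAP 6.8.1 also lists an initial loading dose. If that 4 mg were counted on top of Day 1's 12 mg (an assumption), the ratios would be higher still: 172/14/10 = 122.9% at Day 14 and 284/28/10 = 101.4% at Day 28.

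**The case against.** The best defense is that the SAP makes no numerical mistake: 10 mg/day is right for the full cycle, and the 12 and 8 mg/day phase values stand in the same section. A programmer could use 12 for a patient who has only Days 1-14. That is possible, but no rule says so. The listing is for the first cycle, and 10 is the value named for the first cycle.

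The second argument is that the trigger may never occur. It needs a permanent loperamide stop before Day 28, and most holds are meant to be resumed. The bar on reintroducing discontinued investigational product (SAP 2.3.2) does not itself say that loperamide stops. The constipation route passes through several reduced doses before "If a patient is unable to tolerate once-daily loperamide due to constipation, hold loperamide and discuss subsequent loperamide dosing with the Medical Monitor", so that patient would carry the inflation factor but would not show the 120% of full dosing. The documents give no early-stop rate for Cycle 1. Protocol Table 2 shows 20.4% discontinuing for diarrhea in the loperamide cohort of Study 6201, over a median of 11.63 months. Applied to this trial as an assumption, that is 0.204 × 3 = 0.6 to 0.204 × 5 = 1.0 patients over the whole course, with an unknown share in Cycle 1. This stands: possibly no patient is affected.

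Third, the listing also shows duration, cumulative dose, and highest and lowest daily dose, so a careful reader can recompute the ratio. Doses may be raised or lowered for symptoms, so departures from 100% are expected anyway. Both points are true and limit the harm, but neither makes the listed ratio a correct comparison with plan.

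Finally, a denominator over the days spanned would read 100% for a patient who took everything and stopped on Day 3, or who started on Day 5 and so received 232/280 = 82.9% of the cycle's planned dose. That is a fair caution, and it is a reason to list the share of 280 mg as well.

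**Conclusion.** The concern holds, as a minor point. Read plainly, the SAP gives a wrong ratio to plan for any patient who starts loperamide on Day 1 and stops for good before Day 28. The overstatement is a factor of 1.20 for stops up to Day 14, shrinking to 1.007 at Day 27. This rests on the SAP 3 duration applying to loperamide, on 10 mg/day being the denominator for everyone, and on the initial 4 mg being part of Day 1's schedule.

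Early stoppers would be included. A patient replaced under Protocol 10.4 who took at least one neratinib dose stays in the safety population, the only one the SAP defines. The reach is one column of one listing for 3-5 patients. No endpoint, summary table or decision uses the ratio.

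**What to change.** In SAP 6.8.1, replace the fixed 10 mg/day denominator with the doses planned for the cycle days spanned:

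*relative dose intensity = cumulative actual dose in Cycle 1 / sum of planned daily doses from the first to the last loperamide dose in Cycle 1*

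Count 12 mg for each of cycle Days 1-14 and 8 mg for each of Days 15-28, with cycle day numbered from the first neratinib dose. Full dosing then reads 100% over any span. The late-start examples become 260/260, 224/224 and 232/232, and the 140 mg patient reads 83.3%.

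It is worth adding cumulative actual dose/280 mg as a second column so that early stopping and late starting stay visible: a planned-dose patient who stops on Day 14 shows 168/280 = 60%. State also whether the initial 4 mg is part of Day 1's 12 mg.

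The cost is one formula line and the matching derivation. No new data are needed, and no dose or clinical rule changes.
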